7.1.6.4 Survival Follow-up

Survival Follow-Up will be conducted at each visit during the *Lm* Surveillance period and via a telephone call every 3 months (± 2 weeks) after the *Lm* Surveillance period to determine survival status for all subjects.

7.2 Assessing and Recording Adverse Events

An AE is defined as any untoward medical occurrence in a patient or clinical investigation subject administered a pharmaceutical product and which does not necessarily have to have a causal relationship with this treatment. An AE can therefore be any unfavorable and unintended sign (including an abnormal laboratory finding, for example), symptom, or disease temporally associated with the use of a medicinal product or protocol-specified procedure, whether or not considered related to the medicinal product or protocol-specified procedure. Any worsening (i.e., any clinically significant

adverse change in frequency and/or intensity) of a preexisting condition that is temporally associated with the use of the Sponsor's product, is also an AE.

Changes resulting from normal growth and development that do not vary significantly in frequency or severity from expected levels are not to be considered AEs. Examples of this may include, but are not limited to, onset of menses or menopause occurring at a physiologically appropriate time.

The Sponsor's product includes any pharmaceutical product, biological product, device, diagnostic agent or protocol-specified procedure, whether investigational (including placebo or active comparator medication) or marketed, manufactured by, licensed by, provided by or distributed by Advaxis for human use.

AEs may occur during the course of the use of Advaxis' product in clinical trials or within the follow-up period specified by the protocol, or prescribed in clinical practice, from overdose (whether accidental or intentional), from abuse and from withdrawal.

AEs may also occur in screened subjects during any pre-allocation baseline period as a result of a protocol-specified intervention, including washout or discontinuation of usual therapy, diet, placebo treatment or a procedure.

All AEs will be recorded from the time the consent form is signed through 30 days following cessation of treatment on the Adverse Event CRF forms/worksheets. The reporting timeframe for AEs meeting any serious criteria is described in [Section 7.2.3.1](#).

7.2.1 Overdose

For purposes of this trial, an overdose will be defined as any ADXS11-001 dose exceeding the prescribed dose. No specific information is available on the treatment of overdose of ADXS11-001. In the event of an ADXS11-001 overdose, the subject should be observed closely for signs of toxicity. Appropriate supportive treatment should be provided if clinically indicated.

If an AE(s) is associated with ("results from") the overdose of an Advaxis product, the AE(s) is reported as a SAE, even if no other seriousness criteria are met.

If a dose of Advaxis' product meeting the protocol definition of overdose is taken without any associated clinical symptoms or abnormal laboratory results, the overdose is reported as an AE.

All reports of overdose with and without an AE must be reported within 24 hours to inVentiv Health Clinical Pharmacovigilance (Attn: iHC SAE Reporting; [contact] or email: [contact]).

7.2.2 Reporting of Pregnancy and Lactation to the Sponsor

Although pregnancy and lactation are not considered AEs, it is the responsibility of investigators or their designees to report any pregnancy or lactation in a subject (spontaneously reported to them), including the pregnancy of a male subject's female partner that occurs during the trial or within 120 days of completing the trial completing the trial, or 30 days following cessation of treatment if the subject initiates new anticancer therapy, whichever is earlier. All subjects and female partners of male subjects who become pregnant must be followed to the completion/termination of the pregnancy. Pregnancy outcomes of spontaneous abortion, missed abortion, benign hydatidiform mole, blighted ovum, fetal death, intrauterine death, miscarriage and stillbirth must be reported as serious events (Important Medical Events). If the pregnancy continues to term, the outcome (health of infant) must also be reported.

Such events must be reported within 24 hours of awareness to inVentiv Health Clinical Pharmacovigilance (Attn: iHC SAE Reporting; [contact] or email: [contact]).

7.2.3 Immediate Reporting of Adverse Events to the Sponsor

7.2.3.1 Serious Adverse Events

A serious adverse event is any AE occurring at any dose or during any use of Advaxis' product that:

- Results in death;
- Is life threatening;
- Results in persistent or significant disability/incapacity;
- Results in or prolongs an existing inpatient hospitalization;
- Is a congenital anomaly/birth defect;
- Is a new cancer (that is not a condition of the study);
- Is associated with an overdose;
- Is another important medical event

Progression of the cancer under study is not considered an AE unless it results in hospitalization or death.

Any SAE, or follow up to a SAE, including death due to any cause other than progression of the cancer under study that occurs to any subject from the time the consent is signed through 30 days following cessation of treatment, whether or not related to Advaxis'

product, must be reported within 24 hours to the Sponsor at inVentiv Health Clinical Pharmacovigilance (Attn: iHC SAE Reporting; [contact] or email: [contact]).

Additionally, any SAE, considered by an investigator who is a qualified physician to be related to Advaxis' product that is brought to the attention of the investigator at any time outside of the time period specified above also must be reported immediately to the Sponsor.

SAE reports and any other relevant safety information are to be forwarded to inVentiv Health Clinical Pharmacovigilance (Attn: iHC SAE Reporting; [contact] or email: [contact]).

A copy of all 15 Day Reports and Annual Progress Reports is submitted as required by FDA, European Union (EU), Pharmaceutical and Medical Devices agency (PMDA) or other local regulators. Investigators will cross reference this submission according to local regulations to the Advaxis Investigational Compound Number (IND, CSA, etc.) at the time of submission. Additionally, investigators will submit a copy of these reports to inVentiv Health Clinical Pharmacovigilance (Attn: iHC SAE Reporting; [contact] or email: [contact]) at the time of submission to FDA.

All subjects with SAEs must be followed up for outcome.

7.2.4 Evaluating Adverse Events

An investigator who is a qualified physician will evaluate all AEs according to the NCI CTCAE v 4.0. Any AE that changes CTCAE grade over the course of a given episode will have each change of grade recorded on the AE CRF/worksheets.

All AEs regardless of CTCAE grade must also be evaluated for seriousness.

The following attribution categories ([Table 12](#)) will be used in assessing the relationship between the AE and the study treatment:

Table 12 Attribution Categories

RELATIONSHIP	ATTRIBUTION	DESCRIPTION
Unrelated to investigational agent/intervention	Unrelated	The AE is clearly NOT related to the intervention
	Unlikely	The AE is doubtfully related to the intervention
Related to investigational agent/intervention	Possible	The AE may be related to the intervention
	Probable	The AE is likely related to the intervention
	Definite	The AE is clearly related to the intervention

7.2.5 Sponsor Responsibility for Reporting Adverse Events

All AEs will be reported to regulatory authorities, IRB/IECs and investigators in accordance with all applicable global laws and regulations.

8 STATISTICAL CONSIDERATION

8.1 General Consideration

Descriptive statistics will be employed to evaluate the endpoint and analyze the data. Summary statistics for continuous variables will include mean, standard deviation, median and range. Categorical variables will be presented as frequency counts and percentages; and time-to-event variables will be summarized by Kaplan-Meier (KM) medians and survival plots. Data listings will be created to support tables and present data. The preliminary efficacy analysis will be conducted on the efficacy evaluable population and safety analysis will be performed on the safety population. SAS 9.2 or higher will be used for data analysis. The details of statistical analysis will be described in the Statistical Analysis Plan (SAP). The data will be tabulated and analyzed with respect to patient enrollment and disposition, demographic, and baseline characteristics.

8.2 Sample Size and the Design

This is a multi-center, open-label, 2 stage monotherapy study of ADXS11-001 in subjects with persistent/recurrent, loco-regional or metastatic SCCA of the anorectal canal that was previously treated in the metastatic setting.

Primary Efficacy Measures are:

1. The overall response
2. Progression-Free Survival (PFS)

We employed a 2-stage design for testing these 2 primary efficacy measures. Simon's 2-stage method is not directly applicable because it is for single proportion type endpoint. However, we used Simon's method with null and alternative response rates of 10% in Stage 1 and 20% in Stage 2 to obtain the total sample sizes for both stages and use the Multinomial Two-Stage approach proposed by Benny Zee, *et al* (1999) [24] to obtain the stopping probabilities.

By Simon's method, we need to enroll 31 subjects at Stage 1 and an additional 24 subjects in Stage 2 if 3 or more responses are observed in Stage 1. Based on this sample size plan, we formed the following 2 endpoints, 2-stage framework:

In Stage 1 of the study, we will enroll 31 subjects. The safety and efficacy data of the subjects will be evaluated. After 31 evaluable subjects have been enrolled, further accrual will be temporarily stopped in Stage 1 for an efficacy interim analysis evaluation. If the efficacy from Stage 1 demonstrates a response rate $\geq 10\%$ or 6-month PFS $\geq 20\%$,

the enrollment will re-open to Stage 2. The enrollment will be complete in Stage 2 when an additional 24 evaluable have been accrued (total from Stages 1 and 2 = 55).

The hypothesis testing in Stage 1 is given in the following:

- Stage 1:
 - Null Hypothesis (H_0): Response rates (r_1) <10% and 6-month PFS rate (p_1) <20%;
 - Alternative Hypothesis (H_a): Response rates (r_1) \geq 10% or 6-month PFS rate (p_1) \geq 20%
- Stage 2:
 - Null Hypothesis (H_0): Response rates (r_2) \leq 25% and 6-month PFS rate (p_2) \leq 50%;
 - Alternative Hypothesis (H_a): Response rates (r_2) \geq 25% or 6-month PFS rate (p_2) \geq 50%

Using the Multinomial Two-Stage approach proposed by Benny Zee, *et al* (1999),[\[24\]](#) we simulated 50,000 trials to examine the Type I and II errors under this design assumption. The following estimates, including Type I and II errors, from these simulations are summarized in the following table.

Type I	Type II
Type I Error = 0.03236 ASN for H0 = 32.20192 P(stop early H0) = 0.94992	Power = 0.924

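### The 10% and 20% response rates given in section 8.2 do not generate 31 + 24 subjects; that design matches a Simon minimax design for 10% versus 25%

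*Combined protocol and SAP*

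**What the plan says.** Section 8.2 (Sample Size and the Design) names two primary measures, overall response and PFS. It notes that Simon's method does not apply directly to two endpoints, but uses it "to obtain the total sample sizes for both stages", with "null and alternative response rates of 10% in Stage 1 and 20% in Stage 2". The result is given as "31 subjects at Stage 1 and an additional 24 subjects in Stage 2 if 3 or more responses are observed in Stage 1".

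The section gives no alpha, power, criterion (optimal or minimax) or final critical count out of 55 for this step.

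It then sets a two-endpoint rule. Stage 2 opens if the Stage 1 response rate is at least 10% or 6-month PFS is at least 20%. The Stage 2 hypotheses use 25% for response and 50% for 6-month PFS. Stopping probabilities come from a separate multinomial two-stage simulation, reported as "Type I Error = 0.03236", power 0.924 and "P(stop early H0) = 0.94992". The true rates behind these figures are not stated.

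**The concern.** Simon's two-stage design has one null rate and one alternative rate, and both apply to the whole trial. Giving 10% to one stage and 20% to the other does not describe such a design. The natural repair is to read 10% as the null and 20% as the alternative, but a 10-point difference at these rates normally needs more than 55 subjects.

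This is the only derivation of N in the protocol. A reader would take from it that 55 subjects can separate a 20% response rate from 10% with conventional error rates. If they cannot, the detectable response rate is less favourable than the text implies, and a drug with a true 20% response rate has a substantial chance of missing on response.

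**Working it through.** **Inputs.** From section 8.2: rates 10% and 20%; n1 = 31, n2 = 24, N = 55; continue on 3 or more responses, or on an observed rate of at least 10%. Not stated, so varied here: one-sided alpha 0.05 and 0.10; power 70%, 80% and 90%; optimal and minimax criteria.

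**Formulas.** With stop boundary r1 (stop if responses ≤ r1 of n1) and final boundary r (positive if total > r of N):

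- P(stop early | p) = P(X1 ≤ r1), X1 ~ Bin(n1, p)
- P(positive | p) = Σ over x > r1 of P(X1 = x) × P(X2 > r − x), X2 ~ Bin(N − n1, p)

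Alpha is P(positive) at the null rate and power is P(positive) at the alternative rate.

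**Step 1. The plan's own figures.** The reported average sample number under H0 agrees with the reported stopping probability: 31 + 24 × (1 − 0.94992) = 32.202. The Simon step is not reproduced, as follows.

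**Step 2. Exhaustive search, 10% versus 20%.**

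| One-sided alpha | Power | Optimal n1/N | Minimax n1/N |
|---|---|---|---|
| 0.05 | 70% | 21/66 | 35/56 |
| 0.05 | 80% | 30/89 | 45/78 |
| 0.10 | 70% | 20/50 | 25/40 |
| 0.10 | 80% | 24/65 | 29/56 |
| 0.10 | 90% | 41/99 | 61/86 |

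Alpha 0.05 with 90% power was not searched, but it cannot need fewer than the 78 required for 80%. No row gives 31/55. The nearest is 29/56, which continues on 3 or more and is positive at 9 or more (alpha 0.0989, power 0.802). A sweep of non-standard powers does return 31/55 for 10% versus 20% at alpha 0.05, but only with the power target set at 66.8%.

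**Step 3. Search, 10% versus 25%, alpha 0.05, power 90%.** The minimax design is exactly n1 = 31, N = 55: stop at ≤ 3/31, positive at ≥ 10/55. Alpha is 0.0422, power 0.9006, and P(stop early) at 10% is 0.624. The optimal design is 21/66.

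**Step 4. Response-only results on 31/55.**

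| Continue if | Positive if | Alpha at 10% | Power at 20% | Power at 25% |
|---|---|---|---|---|
| ≥ 4/31 | ≥ 10/55 | 0.042 | 0.668 | 0.901 |
| ≥ 3/31 | ≥ 10/55 | 0.044 | 0.681 | 0.909 |
| ≥ 3/31 | ≥ 9/55 | 0.0925 | 0.791 | 0.952 |
| ≥ 3/31 | ≥ 11/55 | 0.019 | 0.553 | 0.844 |
| ≥ 3/31 | ≥ 14/55 | 0.001 | 0.197 | 0.521 |

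The last row reads the Stage 2 threshold as an observed rate of at least 25% (14/55 = 25.5%).

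**Step 5. Upper bound without assuming a boundary.** Over every pair of stage 1 and final cut-offs on 31/55, the highest power at a true 20% is 0.684 with alpha ≤ 0.05 and 0.798 with alpha ≤ 0.10. Both maxima occur with no early stopping, so any stop rule only lowers them.

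**Step 6. The two Stage 1 response rules.** 3/31 = 9.7%, below 10%; 4/31 = 12.9%. Three responses therefore pass the count rule and fail the percentage rule.

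**The case against.** The strongest reply is that Simon's method supplied only the sample sizes. Section 8.2 says it is not directly applicable, and the trial is judged on response or 6-month PFS. The only power claimed is 0.924, for that two-endpoint rule, and it is not claimed at a true 20% response rate. This stands. A reader might infer from the 67% that the whole trial has about 67% power at a 20% response rate. The documents do not support that: overall power also depends on a PFS rate and a correlation with response that are not given, and the cut-off of 10/55 appears nowhere in the text.

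The second reply is that alpha is not stated, and 10% versus 20% at alpha 0.10 and 80% power gives 29/56, close to 31/55 and with the same count rule of 3 or more. This stands in part. The mismatch is wide at alpha 0.05 and narrow at 0.10. Even so, 31/55 falls just short of 80% at alpha 0.10 (0.798 at best), and an alpha near 0.09 on response alone sits poorly with a reported type I error of 0.032 for an either-endpoint rule, if the simulated null response rate was 10%.

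The third reply is that the 10% versus 25% origin is an inference with loose ends. Its rule is to continue on 4 or more, which fits the percentage rule but not the count rule. At a 10% response rate, 10/55 alone has alpha of 0.042 to 0.044, above the reported 0.032, and the design stops early with probability 0.624 rather than 0.950. So that boundary was probably not what was simulated, if the simulated null was 10%. This also stands, and is why the sponsor must confirm the inputs. It does not restore 10% and 20% as the source of 31 + 24.

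**Conclusion.** The stated inputs are wrong as written. Simon's method does not take one rate per stage, and 10% versus 20% gives 31 + 24 at no standard alpha and power tried. Confidence in this is high. The sizes match exactly the minimax design for 10% versus 25% at one-sided alpha 0.05 and power 90%; that this was the actual source is likely but unconfirmed.

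On response alone, a true rate of 20% would be detected with power of at most 0.68 at alpha 0.05 and 0.798 at alpha 0.10. These bounds need no assumption about cut-offs. The figure of 0.67, a miss about one time in three, assumes a stop at 3/31 and a final cut-off of 10/55. None of these figures is the power of the two-endpoint trial.

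**What to change.** Keep N = 55 and revise section 8.2:

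1. Replace the stage-by-stage rates with one null, one alternative, the alpha, the power and the criterion that generate 31/55. If the sponsor confirms the match, these are 10%, 25%, one-sided 0.05, 0.90 and minimax.
2. State the final response cut-off out of 55 and reconcile it with the Stage 2 hypothesis. A cut-off of 10/55 is an observed 18.2%, which cannot be declared positive against a null that extends to 25%, so inserting it alone would add an inconsistency.
3. Reconcile the Stage 1 count rule (3 of 31) with the percentage rule (4 of 31).
4. State that, under the 10% versus 25% design with 10/55, response-only power at a true 20% is about 67%, and that this is separate from the two-endpoint power.

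The rates and power statement need one paragraph. Settling the final cut-off also means revisiting the Stage 2 hypotheses. No subjects are added; the cost is that the stated detectable response rate becomes 25% instead of 20%.

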2 TRIAL DESIGN

Specific procedures to be performed during this trial, as well as the prescribed times and associated visit windows are outlined in the Schedule of Events- [Section 6.1](#). Details of each procedure are provided in [Section 7.1](#) - Trial Procedures.

This is a multi-center, open-label, 2 stage monotherapy study of ADXS11-001 in subjects with persistent/recurrent, loco-regional or metastatic SCCA of the anorectal canal that was previously treated in the metastatic setting. Stage 1 of the study will evaluate the safety and efficacy of ADXS11-001. After 31 evaluable subjects have been enrolled, further accrual will be temporarily stopped in Stage 1 to complete an interim efficacy

analysis evaluation. If the efficacy from Stage 1 demonstrates a response rate $\geq 10\%$ by either RECIST 1.1 or 6-month progression free survival (PFS) rate $\geq 20\%$, enrollment will re-open to Stage 2. Enrollment will be complete in Stage 2 when an additional 24 evaluable subjects have been accrued (total 55).

Subjects will be treated with intravenous (IV) ADXS11-001 administered over [REDACTED] every 3 weeks at a dose of 5×10^9 CFU for up to 2 years or until a discontinuation criterion is met. A treatment cycle is defined as 9 weeks. Tumor assessments will occur every 9 weeks (Week 8 of every Cycle). Subjects will be monitored for adverse events (AEs) throughout the study; AEs will be graded in severity according to the guidelines outlined in the NCI Common Toxicity Terminology Criteria for Adverse Events (CTCAE) version 4.0.

Safety follow-up will be conducted via telephone call 30 days (± 5 days) after the last ADXS11-001 infusion to confirm the resolution of any ongoing AEs and SAEs. Survival Follow-Up will be conducted at each visit during the Lm Surveillance period and via a telephone call every 3 months (± 2 weeks) after the Lm Surveillance period to determine survival status for all subjects.

The end of the study will be defined as 1 year after the last subject has enrolled on study. However, any ongoing subjects, subjects who are still deriving clinical benefit from ADXS11-001 therapy at the end of their 2-year treatment period or at the end of the study may be enrolled into a separate extension study, as available.

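### The sizing sentence opens Stage 2 at 3 responses among 31, but 3/31 = 9.7% fails the ≥10% response criterion of the Stage 1 go rule, which needs 4

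*Combined protocol and SAP*

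**What the plan says.** Section 8.2 gives the Stage 1 response criterion in two ways.

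- **As a count.** The sizing sentence says that Simon's method requires 31 subjects and then "an additional 24 subjects in Stage 2 if 3 or more responses are observed in Stage 1".
- **As a rate.** The framework that follows says "If the efficacy from Stage 1 demonstrates a response rate" of at least 10%, or a 6-month PFS of at least 20%, then Stage 2 opens. Section 2 states the same thresholds. The hypothesis in Section 3.1 and the Stage 1 hypotheses in Section 8.2 use them too.

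The denominator is fixed: "After 31 evaluable subjects have been enrolled, further accrual will be temporarily stopped in Stage 1 for an efficacy interim analysis evaluation". Section 5.9 replaces non-evaluable subjects to keep the planned number.

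On the sizing inputs, Section 8.2 says "we used Simon's method with null and alternative response rates of 10% in Stage 1 and 20% in Stage 2". It states no alpha, power or optimality criterion for that step, and it says that Simon's single-proportion method does not apply directly to a two-endpoint design. It then reports 50,000 simulated trials with type I error 0.03236, probability of early stopping under the null 0.94992, expected sample size 32.20192 and power 0.924. The true rates used in the simulation are not given.

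**The concern.** A go/no-go rule should give one answer for every possible Stage 1 result. Here the count is met at 3 responses and the rate is not. If 3 of 31 respond and the PFS criterion is also missed, the sizing sentence supports enrolling 24 more subjects and the framework says stop. The trial is open-label (Section 5.2.7) and has no external monitoring committee (Section 8.4), so the sponsor would choose between two written rules with the results in view. What is at stake is whether 24 more patients are enrolled after a Stage 1 that misses the stated rate thresholds.

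**Working it through.** **1. The two criteria at n = 31**

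- 3/31 = 9.68%, below 10%: the count is met, the rate is not.
- 4/31 = 12.90%: both are met.
- PFS route, as a simple proportion: 6/31 = 19.4% fails and 7/31 = 22.6% passes.

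**2. The plan's own figure**

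The stated expected sample size follows from the stated stopping probability: 31 + 24 × (1 − 0.94992) = 32.20192. This shows the table is internally consistent. It does not show whether the simulation continued at 3 or at 4, because the simulated rates are missing. For illustration, with independent endpoints, the probability of stopping at true rates of 5% response and 10% PFS is 0.775 (continue at 3) or 0.904 (continue at 4). At 3% and 10% it is 0.906 or 0.957.

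**3. Probability that the texts conflict**

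The go rule is an OR rule, so a conflict needs exactly 3 responders and at most 6 of 31 progression-free at 6 months. The true rates are assumptions. Two dependence structures bracket the result:

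- *Independent endpoints:* P(X = 3) × P(Y ≤ 6), with X ~ Bin(31, r) and Y ~ Bin(31, p).
- *Nested endpoints* (every responder is progression-free at 6 months): P(X = 3) × P(Z ≤ 3), with Z ~ Bin(28, (p − r)/(1 − r)).

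| True response r / PFS p | P(X = 3) | P(Y ≤ 6) | Independent | P(Z ≤ 3) | Nested |
|---|---|---|---|---|---|
| 10% / 20% | 0.235 | 0.571 | 13.4% | 0.621 | 14.6% |
| 5% / 20% | 0.134 | 0.571 | 7.6% | 0.335 | 4.5% |
| 5% / 10% | 0.134 | 0.969 | 13.0% | 0.943 | 12.6% |

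**4. Response gate alone**

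| True response rate | P(at least 3 of 31) | P(at least 4 of 31) |
|---|---|---|
| 5% | 0.201 | 0.067 |
| 10% | 0.611 | 0.376 |
| 25% | 0.992 | 0.969 |

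**5. Where the 3 may come from**

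An exact Simon search needs an assumed alpha and power.

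- *10% against 25%, one-sided alpha 0.05, power 90%:* the minimax design is exactly n1 = 31 and N = 55, stopping at 3 or fewer and rejecting at more than 9 (alpha 0.0422, power 0.9006). That design continues at 4.
- *10% against 20%, as the sizing sentence reads:* no design with N ≤ 60 reaches power 75% or more at alpha 0.05. The minimax N for 80% power is 78. At alpha 0.10 and power 80% the minimax design is 29 then 56 in total, continuing at 3. There 3/29 = 10.3% would satisfy the rate rule, but that is not the 31/55 plan.

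**6. Effect on the final test**

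Response alone, on the 31/55 design with final cut-off more than 9 of 55:

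| Continue at | Alpha at 10% | Power at 25% |
|---|---|---|
| at least 3 | 0.0440 | 0.909 |
| at least 4 | 0.0422 | 0.901 |

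**The case against.** The best defence is that the operative rule is not ambiguous. The rate rule appears in Sections 2 and 8.2 and matches the hypotheses. The count appears once, in a sizing sentence, for a method the protocol itself says does not apply directly. A natural reading is that the framework governs. That stands as a description of where the conflict lies: a sizing count against a repeated decision rule. It does not remove the conflict, because no sentence gives precedence, the framework is said to be built on that sizing plan, and 3 is the only integer response cut-off in the document.

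Three stronger readings are tempting, and the documents do not support them.

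- *The risk is 23.5%.* That is the probability of exactly 3 responses at a true 10%, before the PFS route is considered. Because either criterion opens Stage 2, the relevant figure is smaller.
- *A true 10% represents an inactive drug.* The Stage 1 null is response below 10% and PFS below 20%, so a true 10% lies in the stated alternative.
- *The stop boundary was certainly misread as the go boundary.* The match to 31/55 is exact, but it takes 25% from the Stage 2 hypotheses and assumes alpha, power and the minimax criterion. It is a likely explanation, not a demonstrated one.

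Rounding 9.68% to a whole percent would also remove the conflict, but the plan has no rounding rule.

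**Conclusion.** The inconsistency is real and rests only on 3/31 being below 10%. It affects the decision when exactly 3 of 31 respond and 6-month PFS is below 20%. The probability of that is about 13–15% at true rates of 10% and 20%, and about 4–13% at 5% response with 10–20% PFS. These figures treat 6-month PFS as a simple proportion with no censoring before 6 months, whereas Sections 8.1 and 8.3.1 treat PFS as censored time-to-event data summarised by Kaplan-Meier.

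A reader might infer that the trial's error rates fail. They do not on this account: for response alone, under the assumed final cut-off, alpha stays below 0.05 with either count and power changes by less than one percentage point. The consequence is an undefined decision about 24 further patients. The reported 0.94992 stopping probability cannot be traced to either cut-off.

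**What to change.** 1. In the Section 8.2 sizing sentence, change the count from 3 to 4, so that it agrees with the ≥10% rule.
2. In Sections 2 and 8.2, state the response gate as at least 4 of 31 evaluable subjects.
3. Keep the PFS gate at ≥20%. It equals at least 7 of 31 only if 6-month PFS is taken as a simple proportion with no censoring before 6 months, so the text should say which estimate is used.
4. Confirm that the simulated stopping probability, type I error and power used the same cut-off, and state the true rates simulated. If the simulation continued at 3, rerun it.

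The cost is a short amendment and no extra patients. The response gate becomes harder to pass: at a true 25% the chance of passing on response alone falls from 0.992 to 0.969, and response-only power falls from 0.909 to 0.901. The amendment should be in place before the interim data are seen.

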3 OBJECTIVES & HYPOTHESIS

3.1 Primary Objectives & Hypothesis

Objective: To evaluate efficacy as measured by the overall response rate and rate of 6 month PFS in subjects with persistent/recurrent, loco-regional or metastatic SCCA of the anorectal canal as determined by RECIST 1.1

- a. **Hypothesis:** ADXS11-001 will produce response rates $\geq 10\%$ or 6 month PFS rates $\geq 20\%$ in subjects with persistent/recurrent, loco-regional or metastatic SCCA of the anorectal canal.
-

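### The printed early-stop probability (0.95) and expected sample size (32.2) cannot come from the stated Stage 1 gate at the 10%/20% null, and the printed Type I error and power cannot be checked

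*Combined protocol and SAP*

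**What the plan says.** Section 8.2 (Sample Size and the Design) takes its sample size from Simon's method, with "null and alternative response rates of 10% in Stage 1 and 20% in Stage 2". It concludes that "we need to enroll 31 subjects at Stage 1 and an additional 24 subjects in Stage 2 if 3 or more responses are observed in" the first stage. It then sets a gate on two endpoints: enrolment reopens if Stage 1 shows response of at least 10% or 6-month PFS of at least 20%. Section 2 (Trial Design) repeats this gate.

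The Stage 1 null is "Response rates (r_1) <10% and 6-month PFS rate (p_1) <20" per cent. The Stage 2 null is response at most 25% and 6-month PFS at most 50%. Its alternative is response at least 25% or PFS at least 50%. Section 3.1 carries only the lower pair: "ADXS11-001 will produce response rates" of at least 10%, or 6-month PFS of at least 20%.

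On operating characteristics, the section says "we simulated 50,000 trials to examine the Type I and II errors under this design assumption", and prints "Type I Error = 0.03236 ASN for H0 = 32.20192 P(stop early H0) = 0.94992" with power of 0.924. It does not give the true rates simulated, the joint distribution of response and PFS, or the number of successes out of 55 that counts as a positive trial. Section 8.3.1 plans tabulated response rates and Kaplan-Meier medians with confidence intervals, and no final test.

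**The concern.** The table tells the reader that an inactive drug would be stopped after 31 subjects about 95% of the time. But the gate thresholds equal the null rates, and passing on either endpoint is enough. Such a gate should let a null drug through often. If 0.95 is wrong at the null, the main protection that the two-stage design offers is much weaker than claimed, and the trial should be expected to enrol well beyond 32 subjects even when the drug does nothing more than the null.

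The second issue is the end of the trial. With two different nulls and no success count, the printed Type I error belongs to no identifiable test. A positive result at 55 subjects could then be defined after the data are seen, in an open-label single-arm study.

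**Working it through.** **Inputs (Section 8.2).** n1 = 31, n2 = 24, total 55. Gate: response ≥10% or 6-month PFS ≥20%. Since 10% of 31 is 3.1 and 20% of 31 is 6.2, the gate is R ≥4 or S ≥7, where R is the number of responders and S the number progression-free at 6 months. The null boundary is 10%/20%.

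**1. The plan's own figures.** Expected N = 31 + 24 × (1 − P(stop)). With P(stop) = 0.94992 this is 31 + 24 × 0.05008 = 32.20192, exactly as printed. The expected size therefore follows from the early-stop probability and is no independent check on it.

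**2. Early stopping at 10%/20%.** Stopping requires R ≤3 and S ≤6.
- P(R ≤3 | 31, 0.10) = 0.624
- P(S ≤6 | 31, 0.20) = 0.571
- Upper bound for any correlation: min(0.624, 0.571) = 0.571, so the gate is passed with probability at least 1 − 0.571 = 0.429.

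| Dependence of R and S | P(stop) | Expected N |
|---|---|---|
| Independent (0.624 × 0.571) | 0.356 | 46.4 |
| Responders nested in 6-month PFS (exact trinomial) | 0.471 | 43.7 |
| Any correlation | ≤0.571 | ≥41.3 |
| Printed | 0.950 | 32.2 |

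**3. Other readings of the gate and null.**
- With the gate of 3 or more responses: P(R ≤2 | 31, 0.10) = 0.389, so P(stop) ≤0.389 and expected N ≥45.7.
- At the Stage 2 null boundary (25%/50%): P(stop) is below 0.001 and expected N is about 55.

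**4. Rates that would give about 0.95.** Both marginal probabilities must reach 0.94992. That requires a true response rate of at most 4.5% and a true PFS rate of at most 11.1%. At 4%/10%, P(stop) is 0.936 (independent) to 0.946 (nested); at 4%/8% it is 0.956 to 0.961.

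**5. Type I error and power.** No final rule is stated, so two were tried with the gate R ≥4 or S ≥7. In each cell the range covers the nested and independent models.

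| Assumed success rule at 55 | P(success) at 10%/20% | P(success) at 25%/50% |
|---|---|---|
| R ≥11 or S ≥18 | 0.031 to 0.036 | at least 0.997 |
| R ≥14 or S ≥28 (Stage 2 rates read as observed cut-offs) | 0.0008 | 0.66 to 0.76 |

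The printed 0.03236 lies inside the first range, so it is not ruled out.

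**6. Source of 31 + 24.** Exact enumeration finds 31/55 as Simon's minimax design for 10% versus 25% (alpha 0.05, power 0.90): stop at ≤3/31, reject at ≥10/55, exact alpha 0.042, power 0.901. Against 20% the same rule has power 0.668. Its continuation count is 4 or more, not 3 or more.

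**The case against.** The Stage 1 null is composite, so a simulation at about 4%/10% lies inside it and would give roughly the printed early-stop probability. That is true, but it rescues the figure only at a point well inside the null that the plan does not name. Error rates for a composite null are normally quoted at its boundary, where 0.95 is out of reach.

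The table might instead belong to a different gate or threshold. The change log records a former PFS threshold of 25%. With 8 or more of 31 at a 25% null, P(S ≤7) = 0.473, so early stopping is still at most 0.473. Requiring both endpoints to pass gives at most 0.898 among the variants tried.

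The objection has more force on Type I error and power. A reader might infer that all four printed figures are refuted. The documents do not support that: a rule of ≥11/55 or ≥18/55 at the same size and gate gives a Type I error of 0.031 to 0.036 and power above 0.924 at 25%/50%. The lower power of 0.66 to 0.76 depends on treating statements about true rates as observed cut-offs, which Section 8.2 does not say. Under that reading Type I error at 10%/20% is 0.0008, stricter than printed.

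A reader might also blame the overlap of the Stage 2 hypotheses for the wrong early-stop figure. The overlap is a drafting fault and moves no operating characteristic.

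Finally, Section 8.1 plans descriptive statistics and leaves details to an SAP, which could supply a final rule. The printed Type I error still needs a null and a rejection rule beside it.

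**Conclusion.** The early-stop probability of 0.95 and expected size of 32.2 are wrong for the stated gate at the Stage 1 null boundary. The bounds there, at most 0.57 and at least 41.3, hold under any correlation and rest only on the stated sizes and on rounding 3.1 and 6.2 up to whole subjects. The narrower ranges, 0.36 to 0.47 and 43.7 to 46.4, also assume independence or nesting. The figures fail at the Stage 2 null boundary too. The reason is the either/or gate placed at the null rates, and it would persist with a single unchanged null.

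Type I error of 0.032 and power of 0.924 are unsupported, not disproved. The null moves from 10%/20% to 25%/50%, the Stage 2 null and alternative share their boundary, and the success count, simulated rates and joint model are missing. This must be corrected, because the stated protection against continuing with an inactive drug is not what the written gate delivers.

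**What to change.** In Section 8.2:
- State one null (response ≤10% and 6-month PFS ≤20%) and one explicit alternative point, with no shared boundary.
- Reconcile the count of 3 or more responses with the 10% threshold (≥4/31), and Simon's 10% versus 20% with the 25% used in Stage 2.
- Give integer boundaries at 31 and at 55, and the assumed joint model for response and 6-month PFS.
- Replace the table with recomputed figures, and align Section 3.1.

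One example at the same 31 + 24: continue if ≥4/31 responders or ≥7/31 progression-free; success if ≥11/55 or ≥18/55. The ranges cover the nested and independent models.

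| Quantity | Value |
|---|---|
| Type I error at 10%/20% | 0.031 to 0.036 |
| P(stop) at 10%/20% | 0.36 to 0.47 |
| Expected N at 10%/20% | 44 to 46 |
| Power if only response reaches its target (25%, PFS 25%) | 0.84 to 0.86 |
| Power if only PFS reaches its target (50%, response 10%) | about 0.997 |

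The sponsor may choose other cut-offs, but must state them. The cost is rewording two sections and a short exact calculation, with no extra patients. The early-stop probability and expected size become less favourable than printed, and so does power when only response improves (0.84 to 0.86 against 0.924). If early stopping near 0.95 at the null is really wanted, the gate itself has to be made stricter.
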